5.3 LIFESTYLE CONSIDERATIONS

Not applicable

5.4 SCREEN FAILURES

Screen failures are defined as participants who consent to participate in the clinical study but are not subsequently randomly assigned to IMP. A minimal set of screen failure information is required to ensure transparent reporting of screen failure participants to meet the Consolidated Standards of Reporting Trials (CONSORT) publishing requirements and to respond to queries from regulatory authorities. Minimal information includes demography, reason for screen failure, eligibility criteria, and any serious adverse event (SAE).

Patients can be rescreened if they do not meet an exclusion criterion. Patients may be rescreened one time if they do not meet the eligibility criteria (I 02) at the Screening Visit (Visit 1) or Randomization Visit (Visit 2) due to a spirometry equipment malfunction, or because the patient is unable to provide sufficient reproducible efforts. Up to 3 total attempts during the screening visit (V1) are allowed for the reasons mentioned above.

Patients who meet eligibility criteria (either meet an exclusion criterion, or who do not meet ([I 02])) may be rescreened only once during the open screening period of the study; a different patient identification number will be issued. Rescreening is not permitted if the patient fails to meet inclusion criteria, except for I 02 (see Section 6.3.1). There is no requirement for a waiting period between the screen-failure date and the rescreening date. The IVRS/IWRS report will flag rescreened patients. Patients that are rescreened must sign a new consent form and all Visit 1 procedures must be repeated.

6 STUDY INTERVENTION

The IMP includes SAR440340 and placebo for SC injection during the course of the study.

6.1 STUDY INTERVENTION(S) ADMINISTERED

Table 2 - Overview of Investigational Medicinal Products administered

Investigational Medicinal Product name	SAR440340	Placebo
Dosage formulation	
Sterile SAR440340 will be provided in one 20 mL vial containing 287 mg of lyophilisate drug product.
 
One vial of lyophilisate drug product (287 mg) is reconstituted by an unmasked site pharmacist or designee (not involved in any study related assessments/activities except preparation of IMP) with 2.5 mL of sterile water for injection resulting in 2.9 mL of 100 mg/mL SAR440340.
 
A volume of 1.5 mL per injection will be withdrawn from the vial. Patients will receive 2 injections per dose.
	
Sterile placebo will be provided in one 20 mL vial containing lyophilisate placebo.
 
One vial of lyophilisate is reconstituted by an unmasked site pharmacist or designee (not involved in any study related assessments/activities except preparation of IMP) with 2.5 mL of sterile water for injection resulting in 2.9 mL IMP.
 
A volume of 1.5 mL per injection will be withdrawn from the vial. Patients will receive 2 injections per dose.

Unit dose strength(s)/Dosage level(s)	300 mg	Not applicable
Route of administration	Subcutaneous injection sites should alternate between the upper thighs, 4 quadrants of the abdomen or the upper arms, so that the same site is not injected twice during consecutive visits	Subcutaneous injection sites should alternate between the upper thighs, 4 quadrants of the abdomen or the upper arms, so that the same site is not injected twice during consecutive visits
Dosing instructions	14±3 days (q2w)	14±3 days (q2w)
Packaging and labeling	SAR440340 will be supplied in a glass vial packed in a kit box. Each kit box will be labeled as required per country requirement.	Matched placebo will be supplied in a glass vial packed in a kit box. Each kit box will be labeled as required per country requirement.

6.1.1 INVESTIGATIONAL MEDICINAL PRODUCT(S)

The investigational medicinal product (IMP) is administered every 14±3 days (q2w).

Investigational medicinal product (IMP) will be administered by the Investigator or designee following clinic procedures and blood collection. Patients should be monitored by site personnel for at least 30 minutes after administration of all IMP injections. The monitoring period may be extended as per country specific or local site specific requirements. Trained personnel and medications should be available to treat anaphylaxis or any severe allergic reaction if it occurs.

Subcutaneous injection sites should alternate between the upper thighs, 4 quadrants of the abdomen or the upper arms, so that the same site is not injected twice during consecutive visits.

6.1.2 NONINVESTIGATIONAL MEDICINAL PRODUCT(S)

Background therapy

Formulation: Dry powder inhaler (DPI), metered dose inhaler (MDI) or pocket nebulizer

Route(s) of administration: Oral inhalation

Dose regimen: As prescribed.

At Screening Visit 1, all patients must be on Standard of Care background therapy, for 3 months prior to Visit 2/Randomization and at a stable dose for at least 1 month prior to the Screening/Visit 1, including either:

- Double therapy: LABA + LAMA or ICS + LABA or ICS + LAMA.
- OR
- Triple therapy: ICS + LABA + LAMA.

Throughout the study, patients should continue their established background therapy for COPD.

Patients must be willing to stay on their established background medication for COPD throughout the duration of the study. After successful management of an acute exacerbation of COPD (e.g. with oral corticosteroids and/or antibiotics), all efforts should be made to resume the initial background COPD treatment regimen if in the investigator's opinion this is medically acceptable. After 1 severe or 2 moderate exacerbations of COPD, dose adjustments in background therapy will be permitted for symptom control and as needed for the remainder of the trial period.

Reliever Medication

Formulation: Dry powder inhaler (DPI), metered dose inhaler (MDI) or pocket nebulizer

Route(s) of administration: Oral inhalation

Dose regimen: As prescribed.

The reliever medication will not be dispensed or supplied by the Sponsor.

Patients may administer albuterol/salbutamol or levalbuterol/levosalbutamol (including ipratropium or ipratropium/short-acting β agonists [SABA] combinations) as needed during the study. Nebulizer solutions may be used as an alternative delivery method.

Study personnel will convert salbutamol/albuterol nebulizer, levosalbutamol/levalbuterol nebulizer or ipratropium or ipratropium/short-acting β agonists [SABA] combination nebulizer, use as shown on the following tables:

Table 3 – Reliever Medication –Salbutamol/Albuterol Nebulizer Solution

Salbutamol/Albuterol Nebulizer Solution -Total Daily Dose (mg)	Number of Puffs*
2.5	4
5.0	8
7.5	12
10	16
*Conversion factor: Salbutamol/Albuterol nebulizer solution (2.5 mg) corresponds to 4 puffs	

- Example of salbutamol/albuterol nebulizer-to-puff conversion: Patient received 3 salbutamol/albuterol nebulizer treatments (2.5 mg/treatment) between 7 and 11 AM. Total daily = 7.5 mg or 12 puffs.

Table 4 - Reliever Medication - Levosalbutamol/Levalbuterol Nebulizer Solution

Levosalbutamol/Levalbuterol Nebulizer Solution -Total Daily Dose (mg)	Number of Puffs*
0.63	2
1.25	4
2.5	8
3.75	12
5	16
*Conversion factor: levosalbutamol/levalbuterol nebulizer solution (1.25 mg) corresponds to 4 puffs	

- Example of levosalbutamol/levalbuterol nebulizer-to-puff conversion: Patient received 3 levosalbutamol/levalbuterol nebulizer treatments (1.25 mg/treatment) between 7 and 11 AM. Total daily = 3.75 mg or 12 puffs.

Table 5 - Reliever Medication - Ipratropium or Ipratropium/short-acting β agonists [SABA] Nebulizer Solutions

Total Daily Dose of Ipratropium (mg) in Ipratropium or Ipratropium/SABA Nebulizer Solutions	Number of Puffs*
0.5	4
1.0	8
1.5	12
2.0	16
*Conversion factor: ipratropium or ipratropium/short-acting β agonists (SABA) nebulizer solution (with 0.5 mg Ipratropium) corresponds to 4 puffs	

- Example of ipratropium or ipratropium/short-acting β agonists [SABA] nebulizer-to-puff conversion: Patient received 3 ipratropium or ipratropium/short-acting β agonists [SABA] nebulizer treatments (0.5 mg Ipratropium/treatment) between 7 and 11 AM. Total daily = 1.5 mg or 12 puffs.

6.2 PREPARATION/HANDLING/STORAGE/ACCOUNTABILITY

Storage and handling

Investigators or other authorized persons (eg, pharmacists) are responsible for storing the IMP/non-investigational medicinal product (NIMP) in a secure and safe place in accordance with local regulations, labeling specifications, policies, and procedures.

Control of IMP storage conditions, especially control of temperature (eg, refrigerated storage) and information on in-use stability and instructions for handling the Sanofi compound must be managed according to the rules provided by the Sponsor in the pharmacy manual.

The expiry date is mentioned on the IMP labels (when required by country regulation), and storage conditions are written on the IMP labels and in the instruction leaflet.

1. The Investigator or designee must confirm appropriate temperature conditions have been maintained during transit for all IMP received and any discrepancies are reported and resolved before use of the IMP.
2. Only participants enrolled in the study may receive IMP and only authorized site staff may supply or administer IMP. All IMP must be stored in a secure, environmentally controlled, and monitored (manual or automated) area in accordance with the labeled storage conditions with access limited to the Investigator and authorized site staff.
3. The Investigator, institution, or the head of the medical institution (where applicable) is responsible for IMP accountability, reconciliation, and record maintenance (ie, receipt, reconciliation, and final disposition records).

4. Further guidance and information for the final disposition of unused IMPs are provided in a Pharmacy manual.

Preparation of IMP

SAR440340 or matching placebo lyophilisate will be reconstituted by an unmasked site pharmacist or designee (not involved in any study related assessments/activities except preparation of IMP) as per instruction provided in study pharmacy manual.

Administration will be performed by blinded nurse or designee as per instruction provided in study pharmacy manual.

Responsibilities

The Investigator, the hospital pharmacist, or other personnel allowed to store and dispense the IMP will be responsible for ensuring that the IMP used in the clinical trial is securely maintained as specified by the Sponsor and in accordance with applicable regulatory requirements.

All IMP will be dispensed in accordance with the Investigator's prescription and it is the Investigator's responsibility to ensure that an accurate record of IMP issued and returned is maintained.

Any quality issue noticed with the receipt or use of an IMP/NIMP/device (deficiency in condition, appearance, pertaining documentation, labeling, expiration date, etc) must be promptly notified to the Sponsor. Some deficiencies may be recorded through a complaint procedure (see [Section 8.3.8](#)).

A potential defect in the quality of IMP/NIMP/device may be subject to initiation of a recall procedure by the Sponsor. In this case, the Investigator will be responsible for promptly addressing any request made by the Sponsor, in order to recall the IMP/NIMP/device and eliminate potential hazards.

Under no circumstances will the Investigator supply IMP/NIMP/device to a third party, allow the IMP/NIMP/device to be used other than as directed by this clinical trial protocol, or dispose of IMP/NIMP/device in any other manner.

6.3 MEASURES TO MINIMIZE BIAS: RANDOMIZATION AND BLINDING

6.3.1 Methods of assigning patients to treatment group

A randomized treatment kit number list will be generated centrally by Sanofi. The investigational product (SAR440340 or matching placebo) will be packaged in accordance with the list. The Sanofi Clinical Supplies team will provide the randomized treatment kit number list to the centralized treatment allocation system (Interactive Voice Response System [IVRS]/Interactive Web Response System [IWRS]). This centralized treatment allocation system will generate the patient randomization list according to which it will allocate the treatments to the patients. Patients who meet the entry criteria will be randomized to receive either SAR440340 or matching

placebo. The Investigator obtains treatment kit number at randomization and subsequent scheduled visits via an IVRS/IWRS that will be available 24 hours a day. Patients will be randomized in a 1:1 ratio to receive SC administrations of either:

- SAR440340 300 mg q2w
- Matching placebo for SAR440340.

Investigational medicinal products will be dispensed at the study visits summarized in SoA ([Section 1.3](#)).

Returned IMP should not be re-dispensed to the participants.

Patients can be rescreened if they do not meet an exclusion criterion. Patients may be rescreened one time if they do not meet the eligibility criteria ([I 02](#)) at the Screening Visit (Visit 1) or Randomization Visit (Visit 2) due to a spirometry equipment malfunction, or because the patient is unable to provide sufficient reproducible efforts. Up to 3 total attempts during the screening visit (V1) are allowed for the reasons mentioned above.

Patients who meet exclusion criteria or who do not meet [I 02](#) as specified above, may be rescreened only once during the open screening period of the study. Rescreening is not permitted if the patient fails to meet inclusion criteria (except for [I 02](#), as described above). For rescreening, see [Section 5.4](#).

Randomization will be stratified by Screening/Visit 1 eosinophil count (see below) and by country.

To ensure scientific validity, alerts will be built into the IVRS/IWRS to control the number of patients enrolled into each stratification group, as follows:

1. Eosinophil <250 /mm³: approximately 50% (170) patients
2. Eosinophil ≥ 250 /mm³: approximately 50% (170) patients

6.3.2 Methods of blinding

SAR440340 and matching placebo will be provided in treatment kits indistinguishable in appearance and will be labeled with a treatment kit number. The randomized treatment kit number list will be generated by Sanofi.

In accordance with the double-blind design, study patients, Investigators, and study site personnel (except the personnel who conduct the reconstitution of the IMP and preparation of syringes for injection) will remain blinded to study treatment and will not have access to the randomization (randomized treatment kit number) except under circumstances described in [Section 6.3.3](#).

To maintain blinding, the personnel involved with dose preparation will be required to agree not to reveal to other study personnel the type of IMP solution (SAR440340 versus placebo) in the vials/syringes.

6.3.3 Randomization code breaking during the study

In case of an AE, the code must only be broken in circumstances when knowledge of the IMP is required for treating the patient.

Code breaking can be performed at any time by using the proper module of the interactive response technology (IRT) and/or by calling any other phone number provided by the Sponsor for that purpose. If the blind is broken, the Investigator must document the date, time of day, and reason for code breaking.

Patient withdrawal will only occur when the code break call is made at the site level, not the study level. This means that if the Emergency Unblinding transaction is performed by the Investigator (ie, at the site level), then the patient will be withdrawn from treatment. However, if the Emergency Unblinding transaction is performed by the Global Safety Officer (GSO) (ie, at the study level, as the GSO is not site based), then the patient will not be withdrawn from treatment.

Patients who are withdrawn from treatment should be encouraged to remain in the study and the Investigator should discuss with them the key visits to attend (see [Section 7.2](#)).

6.4 STUDY INTERVENTION COMPLIANCE

The Investigator or pharmacist will also keep accurate records of the quantities of the IMP dispensed, used, and unused. The product accountability and inventory form is to be updated each time investigational product is dispensed. The study monitor will periodically check the supplies of the IMP held by the Investigator or pharmacist to verify accountability.

Treatment kit number has to be recorded on the appropriate page of the electronic Case Report Form (eCRF) and also on the product accountability and inventory form.

All used, partially used, or unused treatments will be destroyed according to the standard practice at the site or per local regulations. A detailed treatment log of the IMP will be established with the Investigator or other personnel designated by the Investigator, and countersigned by the Investigator and the Monitoring Team. Confirmation of destruction will be provided to the Sponsor.

For NIMP not provided by the Sponsor, tracking, reconciliation and destruction will be managed according to local regulation.

6.5 CONCOMITANT THERAPY

Any medication or vaccine (including over-the-counter or prescription medicines, vitamins, and/or herbal supplements) that the participant is receiving at the time of enrollment or receives during the study must be recorded along with:

- Reason for use
- Dates of administration including start and end dates
- Dosage information including dose and frequency

The following concomitant treatments are not permitted during the screening or treatment phases:

- Systemic steroids (except when used to treat exacerbations)
Note: one short-term course of systemic corticosteroids (up to 6 days) is permitted in 24 weeks, when medically necessary for reasons not related to AECOPD, eg. in the case of severe poison ivy exposure.
- PDE-4 inhibitor such as roflumilast
- Methylxanthines (theophylline, aminophyllines)
- Leukotriene receptor antagonists or leukotriene synthesis inhibitors
- Lipoxygenase inhibitors
- Anti-IL5 mAb (eg, benralizumab; mepolizumab)
- Anti-IgE therapy (eg, omalizumab)
- Anti-IL4R mAb (eg, dupilumab)
- Systemic immunosuppressants (eg, methotrexate, any anti-TNF mAbs, B and/or T cell targeted immunosuppressive therapies)
- Bronchial thermoplasty
- Intravenous immunoglobulin (IVIg) therapy
- Live Attenuated Vaccines: refer to Appendix 7: List of Prohibited Live Attenuated Vaccines, [Section 10.7](#).
- β -adrenergic receptor blockers (except for a selective β -1 adrenergic receptor blocker used with dose stable 1 month prior to Visit 1)
- COPD relievers other than salbutamol/albuterol, levosalbutamol/levalbuterol or ipratropium: their use is not recommended during the study period. In case of use in exceptional circumstances (eg, prescribed by a physician not participating in the study), their use will be documented in the patient's file and reported in the eCRF.
- Other investigational drugs

Note: The following is a list of permitted concomitant medications during the study:

- Antihistamines are permitted as concomitant medication
- Ocular, intranasal, and topical corticosteroids are permitted during the study.

6.6 DOSE MODIFICATION

Not applicable for this study.

6.7 INTERVENTION AFTER THE END OF THE STUDY

Not applicable

7 DISCONTINUATION OF STUDY INTERVENTION AND PARTICIPANT DISCONTINUATION/WITHDRAWAL

Withdrawal of consent for treatment (ie, treatment discontinuation at patient request) should be distinguished from (additional) withdrawal of consent for follow-up visits and from withdrawal of consent for non-patient contact follow-up (eg, medical record checks). The site should document any case of withdrawal of consent.

7.1 DISCONTINUATION OF STUDY INTERVENTION

The IMP should be continued whenever possible.

In case the IMP is stopped, it should be determined whether the stop can be made temporarily; permanent IMP discontinuation should be a last resort. Any IMP discontinuation must be fully documented in the CRF or eCRF. In any case, the patient should remain in the study as long as possible.

7.1.1 Permanent discontinuation

Permanent intervention discontinuation is any intervention discontinuation associated with the definitive decision from the Investigator not to re-expose the patient to the IMP at any time during the study, or from the patient not to be re-exposed to the IMP whatever the reason.

List of criteria for permanent treatment discontinuation

The patients may withdraw from treatment with the IMP if they decide to do so, at any time and irrespective of the reason, or this may be the Investigator's decision. All efforts should be made to document the reason(s) for treatment discontinuation and this should be documented in the eCRF.

Patients must be withdrawn from the study for the following reasons:

- At their own request or at the request of their legally authorized representative (legally authorized representative means an individual or judicial or other body authorized under applicable law to consent on behalf of a prospective patient to the patient's participation in the procedure(s) involved in the research).
- If, in the Investigator's opinion, continuation in the study would be detrimental to the patient's well-being.
- At the specific request of the Sponsor.
- In the event of a protocol deviation, at the discretion of the Investigator or the Sponsor.
- Pregnancy.
- Anaphylactic reaction or systemic allergic reactions or acute allergic reactions that are related to IMP and require immediate treatment (Appendix 14: Definition of anaphylaxis, see [Section 10.15](#)).

- Diagnosis of a malignancy during study, excluding carcinoma in situ of the cervix, or squamous or basal cell carcinoma of the skin.
- Any situation that meets permanent discontinuation rule as outlined in Appendix 6: Liver and other safety: suggested actions and follow-up assessments (Appendix 6, [Section 10.6](#)).
- Any opportunistic infection, such as TB or other infections whose nature or course may suggest an immunocompromised status (Appendix 15: List of Opportunistic Infections, See [Section 10.16](#)).
- Serum ALT >3 ULN and total bilirubin >2 ULN (Appendix 6, see [Section 10.6](#)).
- Serum ALT >5 ULN if baseline ALT \leq 2 ULN or ALT >8 ULN if baseline ALT >2 ULN (Appendix 6, see [Section 10.6](#)).

Any abnormal laboratory value or ECG parameter will be immediately rechecked for confirmation before making a decision of permanent discontinuation of the IMP for the concerned patient.

See the SoA ([Section 1.3.2](#)) for data to be collected at the time of intervention discontinuation and follow-up and for any further evaluations that need to be completed.

Handling of participants after permanent intervention discontinuation

Patients who withdraw from study treatment (prior to completing the planned duration of IMP treatment) will perform, as soon as possible, the early treatment discontinuation visit (ETD) with all assessments normally planned for the EOT visit, to assure a complete clinical assessment in close temporal proximity to the premature termination of study treatment is available. In addition, and to allow assessment of patient outcomes over the stipulated study period, patients will be asked and encouraged to complete all remaining study treatment visits, and participate in all safety follow-up assessments according to the visit schedule with a +/-5 day window. For such patients the assessment schedule will be reduced (See study flowchart for patients after permanent treatment discontinuation in [Section 1.3.2](#)) and alternate visits during the planned treatment period may be conducted by phone (those with odd visit numbers, except for the planned EOT), as can visits F1 and F2.

Under exceptional circumstances when a patient cannot come to the site for a scheduled visit, a phone contact can be made. During the phone contact, at least information about AEs, concomitant medication and COPD exacerbation events should be collected.

Participants will be followed-up according to the study procedures specified in this protocol up to the scheduled date of study completion (ie, EOS, see [Section 1.3](#)), or up to recovery or stabilization of any AE to be followed-up as specified in this protocol, whichever comes last.

All cases of permanent treatment discontinuation must be recorded by the Investigator in the appropriate pages of the CRF or eCRF when considered as confirmed.

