1.3 SCHEDULE OF ACTIVITIES (SOA)

The Schedule of Activities (SoA) for patients who complete the planned treatment is described in Section 1.3.1. Patients who withdraw treatment must complete the Early Treatment Discontinuation (ETD) visit and follow the assessment in Section 1.3.2 for the remaining visits.

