7.2 PARTICIPANT DISCONTINUATION/WITHDRAWAL FROM THE STUDY

A participant may withdraw from the study at any time at his/her own request, or may be withdrawn at any time at the discretion of the Investigator for safety, behavioral, compliance, or administrative reasons.

- If the participant withdraws consent for disclosure of future information, the Sponsor may retain and continue to use any data collected before such a withdrawal of consent.
- If a participant withdraws from the study, he/she may request destruction of any samples taken and not tested, and the Investigator must document this in the site study records. The investigator should also inform the Sponsor that appropriate actions are taken regarding these samples.
- See SoA ([Section 1.3.2](#)) for data to be collected at the time of study discontinuation and follow-up and for any further evaluations that need to be completed.

Patients who withdraw from study treatment (prior to completing the planned duration of IMP treatment) will perform the ETD visit and will be asked and encouraged to complete all remaining study treatment visits (For details, see [Section 1.3.2](#) and [Section 7.1.1](#)). The value of all their study data collected during their continued involvement will be emphasized as important to the public health value of the study.

All study withdrawals should be recorded by the Investigator in the appropriate screens of the CRF or e-CRF and in the patient's medical records. In the medical record, at least the date of the withdrawal and the reason should be documented.

In addition, a patient may withdraw his/her consent to stop participating in the study. Withdrawal of consent for intervention should be distinguished from withdrawal of consent for follow-up visits and from withdrawal of consent for non-patient contact follow-up, eg, medical record checks. The site should document any case of withdrawal of consent.

Participants who have withdrawn from the study cannot be re-randomized/reallocated (treated) in the study. Their inclusion and intervention numbers must not be reused.

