8.3.1 Adverse event of special interest

An adverse event of special interest (AESI) is an AE (serious or nonserious) of scientific and medical concern specific to the Sponsor's product or program, for which ongoing monitoring and immediate notification by the Investigator to the Sponsor is required. Such events may require further investigation in order to characterize and understand them. Adverse events of special interest may be added, modified or removed during a study by protocol amendment.

For these AESIs, the Sponsor will be informed immediately (ie, within 24 hours), per SAE notification described [Section 8.3.2](#), even if not fulfilling a seriousness criterion, using the screens in the eCRF.

Anaphylactic reactions, systemic allergic reactions that require treatment (refer to [Section 10.15](#) for definition of anaphylaxis).

- Anaphylactic reactions, systemic allergic reactions that require treatment (refer to [Section 10.15](#) for definition of anaphylaxis).
- Severe injection site reactions (ISR) that last longer than 24 hours

Note: A severe ISR (for AE reporting) is any event that meets one of the following criteria:

- With a diameter of at least 10 cm.
- Impacting daily activities.
- With ulceration or necrosis.
- For which operative intervention is required.
- Any infection meeting at least one of the following criteria:
 - Any serious infection (SAE).
 - Requires parenteral (IV, intramuscular, SC) antimicrobial therapy
Note: Antimicrobial therapy refers to antibiotic, antiviral, and antifungal agents.
 - Requires oral antimicrobial therapy for longer than 14 days.
 - Is a parasitic infection.
 - Is an opportunistic infection (see Appendix 15: List of Opportunistic Infections, [Section 10.16](#)).
- Significant ALT elevation.
 - ALT >3 x the upper limit of normal (ULN) associated with Total Bilirubin >2 x ULN;
or
 - ALT >5 x ULN in patients with baseline ALT ≤2 x ULN; or
 - ALT >8 x ULN if baseline ALT >2 x ULN.
- Malignancy
- Pregnancy of a female patient entered in a study as well as pregnancy occurring in a female partner of a male patient entered in a study with IMP/NIMP;
 - Pregnancy occurring in a female patient entered in the clinical trial or in a female partner of a male patient entered in the clinical trial. It will be qualified as an SAE only if it fulfills one of the seriousness criteria (see Appendix 3 [[Section 10.3](#)]).
 - In the event of pregnancy in a female participant, IMP should be discontinued.

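### Protocol 7.1.1 orders withdrawal from the study for seven safety events where the surrounding rules call for stopping IMP and keeping the patient in follow-up (wording correction)

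*Protocol*

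**What the plan says.** Protocol 7.1.1 sits within 7.1, on discontinuation of study intervention. Its list is headed as criteria for permanent treatment discontinuation, yet the sentence introducing the bullets reads "Patients must be withdrawn from the study for the following reasons". Eleven bullets follow. Directly after them, the protocol requires abnormal laboratory or ECG values to be rechecked "before making a decision of permanent discontinuation of the IMP for the concerned patient".

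The general rules on patients who stop IMP are these:

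- Protocol 1.3: "Patients who withdraw treatment must complete the Early Treatment Discontinuation (ETD) visit and follow the assessment in Section 1.3.2 for the remaining visits".
- Protocol 6.3.3, on code breaking: "Patients who are withdrawn from treatment should be encouraged to remain in the study".
- Protocol 7.1: "In any case, the patient should remain in the study as long as possible".
- Protocol 7.1.1, on handling after permanent discontinuation: "patients will be asked and encouraged to complete all remaining study treatment visits". Follow-up runs to the scheduled end of study or until adverse events resolve or stabilize, whichever is later.
- Protocol 7.2: such patients "will perform the ETD visit and will be asked and encouraged to complete all remaining study treatment visits". The same section allows, but does not require, the Investigator to withdraw a participant from the study for safety.

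The opening of Protocol 7 asks sites to keep withdrawal from treatment distinct from withdrawal from follow-up.

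SAP 2.4.4.1 includes off-treatment exacerbations up to the planned treatment duration in the primary analysis. Observation is cut at last contact only when a patient leaves the study, and such a patient is then classed as having missing exacerbation data.

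**The concern.** Stopping IMP and leaving the study are separate acts in this protocol, and the primary analysis depends on the difference. The lead-in merges them and uses mandatory language. It is an operative instruction to sites, placed where an investigator would look after a safety event.

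A site that applied it literally would end scheduled visits for a patient with, say, an opportunistic infection or an ALT rise. Exacerbations between that date and the planned end of treatment would then go unrecorded. The data loss would be avoidable and would follow a safety event, so it need not be random with respect to outcome or arm.

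**Working it through.** **Step 1. Sort the eleven bullets.**

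- Four are request or discretion items: own request, Investigator's opinion, Sponsor's request, protocol deviation. Each can be a genuine reason to leave the study and is not disputed.
- Seven are safety events: pregnancy; IMP-related allergic reaction; malignancy; any Appendix 6 rule; opportunistic infection; ALT >3 ULN with bilirubin >2 ULN; ALT >5 or >8 ULN depending on baseline. 4 + 7 = 11.

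**Step 2. Set the lead-in against the general rules.** A patient withdrawn from the study cannot complete the remaining visits under Section 1.3.2 (Protocol 1.3), remain in the study as long as possible (7.1), or be followed to the scheduled end of study (7.1.1). Section 7.2 makes study withdrawal for safety optional; the lead-in makes it compulsory. The conflict applies to all seven safety bullets.

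**Step 3. Look for a rule elsewhere that requires study withdrawal.**

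| Safety bullet | Text elsewhere in the protocol |
|---|---|
| Pregnancy | 8.3.1: "In the event of pregnancy in a female participant, IMP should be discontinued"; Table 6 and Appendix 4 agree |
| Allergic reaction | Table 6: study treatment permanently stopped |
| Opportunistic infection | Table 6: study medication permanently stopped |
| Appendix 6 rule and two ALT rules | Appendix 6 monitors liver tests after IMP is stopped; its flowcharts are not visible in the text available |
| Malignancy | Table 6 covers monitoring and reporting only; the general rules apply |

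None of these requires study withdrawal. They fit the IMP-stop reading, but the conflict itself comes from Step 2.

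**Step 4. Trace the consequence in the SAP.** For a patient who stops IMP and stays, events and time count to the planned end of treatment. For a patient withdrawn from the study, both stop at last contact, and the remaining period is handled only in the multiple-imputation, control-based and tipping-point sensitivity analyses.

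**Step 5. Check whether power is at issue.** The inputs are those of Protocol 9.2: 170 per arm, dispersion k = 1.5, two-sided 5%, the stated monthly accrual, and drop-out of 9%, 15% and 20% by Weeks 12, 24 and 52. Entry is taken as uniform within each month and drop-out as linear between the stated weeks. Information per arm = 170 × mean[μ/(1 + kμ)], with μ = annual rate × weeks/52. The variance of the log rate ratio is the sum of the two reciprocals, and power = Φ(|ln(1 − reduction)|/SE − 1.96).

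- The plan's figures reproduce: mean exposure 35.5 (SD 12.8) weeks, and power at a 45% reduction of 81.6%, 85.2% and 88.8% for placebo rates 1.0, 1.2 and 1.5. For rate 1.0, SE = 0.2089 and 0.5978/0.2089 − 1.96 = 0.902, which gives 81.6%.
- If the withdrawals fall within the planned 20% drop-out, power is unchanged.
- If they came on top, in both arms, power at a 45% reduction falls as shown below. The percentages and stop weeks are assumptions without a source in the documents.

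| Extra withdrawn (assumed) | Points lost over placebo rates 1.0 to 1.5 and a stop at Week 12 or 20 |
|---|---|
| 1% | 0.1 to 0.2 |
| 2% | 0.2 to 0.4 |
| 5% | 0.4 to 1.0 |

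The lowest value is 80.6% (rate 1.0, 5% at Week 12): SE = 0.2117 and 0.5978/0.2117 − 1.96 = 0.864.

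**The case against.** The best reply is that the documents already resolve the slip. The heading and the text on both sides of the list speak of treatment or IMP, and the parent section says the patient should stay. A site would have to disregard several clear statements to do harm. This stands, and it is why the point is a wording correction. It does not make the sentence right: a mandatory instruction that the rest of the protocol contradicts should not be left for sites to interpret.

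A reader might infer that the event-specific passages in 8.3.1, Table 6 and Appendices 4 and 6 directly contradict the lead-in. They do not. They say IMP is stopped, without saying that only IMP is stopped, and leaving the study also stops IMP. Liver monitoring and pregnancy follow-up could in principle continue after study withdrawal.

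A reader might also infer that study withdrawal after a safety event is forbidden. It is not. Section 7.2 permits it, and continued attendance is mostly encouraged; among the general rules only Protocol 1.3 uses mandatory wording. The error lies in making withdrawal compulsory.

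Finally, the two ALT bullets each cite Appendix 6, which also has its own bullet. Seven is therefore a count of bullets and may overstate the number of distinct triggers.

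**Conclusion.** The lead-in is wrong as written for the seven safety bullets. Confidence on the text is high, because the conflict is with the list's own heading, the sentence after it and the general follow-up rules. The consequence is modest and conditional on a site following the sentence literally. Patients handled that way would still contribute events and time up to last contact, and the planned sensitivity analyses would test robustness to the loss, but they cannot recover the unobserved exacerbations.

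The documents give no rate for the listed events, so neither the number affected nor any bias can be derived. A reader might infer that the primary result would be biased or the trial underpowered. The documents do not support either; the power scenarios rest on assumed inputs and show a negligible effect. This is an optional, inexpensive correction.

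**What to change.** Split the list in Protocol 7.1.1. Put the seven safety bullets under a lead-in such as: *Permanently discontinue IMP in any patient with one of the events below. Ask and encourage the patient to remain in the study, with follow-up per Section 1.3.2 and the handling rules that follow, subject to Section 7.2.* This keeps the encouragement wording and leaves both the patient's right to withdraw and the Investigator's safety discretion intact.

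Leave the four request or discretion bullets as possible reasons for IMP discontinuation or for study withdrawal, with the site recording which applies, as the opening of Section 7 requires.

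The cost is one new sentence and a divided list, by site clarification or at the next amendment. The stopping criteria, sample size and analysis stay as they are.
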